5.4.1 Dose Modification Explained

Subjects are permitted dose reduction(s) to a minimum dose of 20 mg/m^2 (40 mg/m^2 /day) in 5 mg/m² (10 mg/m^2 /day) steps. A maximum of three dose reductions in decrements of 5 mg per square meter are allowed for toxicity to a minimum dose of 20 mg/m^2 . Do not escalate dose once it has been reduced. Refer to Table 2 located in this sub-section.

Table 2: TAS-102 Dose Modification Table

| tot at white | 1 | Dosage in | An and a second | Tablets | per dose | Cards I | oer Cycle |
|----------------------------|--------------------------|-----------------------------|--------------------------|---------------------|---------------------|---------|-----------|
| TAS-102 Dose (2x daily) | BSA (m ²) | mg (2x daily) | Total daily dose (mg) | 15 mg | 20 mg | 15 mg | 20 mg |
| Level 1 Dose Red | uction: From 3 | 5 mg/m ² to 30 | mg/m ² | | | | |
| 30 mg/m^2 | < 1.09 | 30 | 60 | 2 | 0 | 2 | 0 |
| | 1.09 - 1.24 | 35 | 70 | 1 | 1 | 1 | 1 |
| | 1.25 - 1.39 | 40 | 80 | 0 | 2 | 0 | 2 |
| | 1.40 - 1.54 | 45 | 90 | 3 | 0 | 3 | 0 |
| | 1.55 - 1.69 | 50 | 100 | 2 | 1 | 2 | 1 |
| | 1.70 - 1.94 | 55 | 110 | 1 | 2 | 1 | 2 |
| | 1.95 - 2.09 | 60 | 120 | 0 | 3 | 0 | 3 |
| | 2.10 - 2.28 | 65 | 130 | 3 | 1 | 3 | 1 |
| | ≥ 2.29 | 70 | 140 | 2 | 2 | 2 | 2 |
| Level 2 Dose Redu | ection: From 30 | 0 mg/m ² to 25 | mg/m ² | | | | |
| 25 mg/m^2 | < 1.10 | 25 ^a | 50 ^a | 2 (PM) ^a | 1 (AM) ^a | 2 | 1 |
| | 1.10 - 1.29 | 30 | 60 | 2 | 0 | 2 | 0 |
| | 1.30 - 1.49 | 35 | 70 | 1 | 1 | 1 | 1 |
| | 1.50 - 1.69 | 40 | 80 | 0 | 2 | 0 | 2 |
| | 1.70 - 1.89 | 45 | 90 | 3 | 0 | 3 | 0 |
| | 1.90 - 2.09 | 50 | 100 | 2 | 1 | 2 | 1 |
| | 2.10 - 2.29 | 55 | 110 | 1 | 2 | 1 | 2 |
| | \geq 2.30 | 60 | 120 | 0 | 3 | 0 | 3 |
| Level 3 Dose Redu | iction: From 25 | 5 mg/m ² to 20 i | mg/m ² | | | | |
| 20 mg/m^2 | < 1.14 | 20 | 40 | 0 | 1 | 0 | 1 |
| | 1.14 - 1.34 | 25 ^a | 50 ^a | 2 (PM) ^a | 1 (AM) ^a | 2 | 1 |
| | 1.35 - 1.59 | 30 | 60 | 2 | 0 | 2 | 0 |
| | 1.60 - 1.94 | 35 | 70 | 1 | 1 | 1 | 1 |
| | 1.95 - 2.09 | 40 | 80 | 0 | 2 | 0 | 2 |
| | 2.10 - 2.34 | 45 | 90 | 3 | 0 | 3 | 0 |
| | ≥ 2.35 | 50 | 100 | 2 | 1 | 2 | 1 |

^a At a total daily dose of 50 mg, patients should take 1 x 20-mg tablet in the morning and 2 x 15-mg tablets in the evening.

BSA=body surface area (calculate to 2 decimal places)

5.4.2 Non-Hematologic Toxicity

Refer to Table 3 located in this sub-section.

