These toxicities can be AEs or laboratory abnormalities such as hepatobiliary or renal laboratory findings.

| Grade ^a | Dose Hold/Resumption within a 28-day Treatment Cycle | Dose Adjustment for Next Cycle |
|--------------------------------|--|-----------------------------------|
| Grade 1 or 2 | | |
| Any occurrence | Maintain treatment at the | None |
| | same dose level | |
| Clinically concerning or treat | tment-related Grade 3 ^b or high | er |
| 1st, 2nd, or 3rd | Suspend treatment until | Reduce by 1 dose level from |
| occurrence | Grade 0 or 1 | the previous level |
| | | |
| 4th occurrence | Discontinue treatment | Discontinue treatment |

Table 3: TAS-102 Dose Modification Schedule for Non-hematologic Toxicities

a Note: For toxicities (AEs or laboratory abnormalities) considered unlikely to become serious or life-threatening (including, but not limited to, fatigue, alopecia, changes in libido, and dry skin), subjects may continue on study medication at the same dose without reduction or interruption at the discretion of the Investigator (irrespective of grade).

b Except for Grade 3 nausea and/or vomiting controlled by aggressive antiemetic therapy or diarrhea responsive to antidiarrheal medication. If there is any uncertainty about continuing study medication or resuming study medication in a subject with Grade \geq 3 non-hematologic toxicities, the case must be discussed with the UFHCC Data and Safety Integrity Committee (DISC) prior to continuing treatment.

5.4.3 Hematologic Toxicity

Obtain complete blood cell counts prior to and on Day 15 of each cycle.

Do not initiate the cycle of LONSURF[®] until:

- Absolute neutrophil count (ANC) is greater than or equal to 1,500/mm³ or febrile neutropenia is resolved
- Platelets are greater than or equal to 75,000/mm³
- Grade 3 or 4 non-hematological adverse reactions are resolved to Grade 0 or 1

Within a treatment cycle, withhold LONSURF[®] for any of the following:

- Absolute neutrophil count (ANC) less than 500/mm³ or febrile neutropenia
- Platelets less than 50,000/mm³
- Grade 3 or 4 non-hematological adverse reactions

After recovery, resume LONSURF[®] after reducing the dose by 5 mg/m²/dose from the previous dose level, if the following occur:

- Febrile neutropenia

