11.2 Safety Analysis

Subjects will be examined and graded each cycle for subjective/objective evidence of developing toxicity according to NCI-CTCAE version 4.03 toxicity criteria. Incidence tables will be generated to summarize incidence of subjects reporting at least one episode of each specific adverse event, incidence of adverse events causing withdrawal, and incidence of serious adverse events. Subjects will have laboratory values assessed prior to and on Day 15 of each cycle.

Adverse event data and corresponding toxicity grades during treatment and during long-term follow-up will be summarized in the form of tables. Incidence tables will be generated to summarize incidence of subjects reporting at least one episode of each specific adverse event, incidence of adverse events causing withdrawal and incidence of serious adverse events. The total number of episodes for each event reported (Frequency Table), the severity and attribution to study therapy of each episode reported (Severity Table and Attribution Table) will also be displayed. Listings of adverse events by subjects will include the time to onset, the duration of each event, the severity of each event, and the relationship of the event to study therapy, whether it was a serious event, and whether it caused withdrawal. Safety data will be summarized for the overall subject group and by dose levels. Dose-toxicity curves will be fitted to the final data to estimate the toxicity rates of each dose levels.

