12.1 Sample Size Determination

This is a pilot phase II single-arm study, with a primary endpoint of progression-free survival (PFS), to evaluate efficacy of TAS-102. Additional objective of the study is to evaluate the feasibility and safety of a regimen of daily TAS-102 administered to subjects with metastatic or unresectable pancreatic adenocarcinoma after progression through or intolerance to first- or second-line chemotherapy. The primary efficacy analysis will be an intent-to-treat comparison of the PFS curve with a reference historical control. From past studies³, the median PFS and/or time to progression (TTP) for subjects with metastatic or unresectable pancreatic adenocarcinoma in the second line of treatment is variable ranging from 6 weeks to 22 weeks. Assuming exponential distributions on PFS on both current study population and the referent population, a sample size of 33 evaluable subjects who will receive the same level of dose will ensure to have at least 80% power to detect an improvement of 3 weeks of median PFS (i.e. from 6 weeks to 9 weeks). The sample size and power derivations were based on one-sample log rank test by Wu $(2015)^{14}$ at one-sided significance level of 0.10. It is assumed that the survival time distributions of both groups (historical and this proposed experiment groups) are approximately the Weibull distribution with a shape parameter of ~ 1.0 . Accounting for about $\sim 10\%$ ineligible/inevaluable subjects, the total number of subjects to be accrued to this cohort will be 37, which is expected to be completed within 24 months. Assuming at least the last evaluable subject derives benefit from the anticipated maximal number of 6 cycles, the length of the entire treatment study will be approximately 30 months.

A subject is considered eligible for toxicity evaluation if they have received at least one dose of TAS-102.

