12.3 Primary and Secondary Endpoint Efficacy Analysis

The primary endpoint to this study will be to determine progression-free survival following TAS-102 therapy. Kaplan-Meier mean estimates and survival curves of progression-free survival rates will be calculated.

A secondary endpoint of this study will be overall survival/TTP following treatment with TAS-102. Kaplan-Meier estimates and survival curves will be calculated. Other secondary endpoints include response rates, clinical benefit rate (CR + PR + SD), toxicities, reversibility of toxicities, and compliance with intended treatment will also be estimated along with exact 95% binomial confidence intervals.

No multiplicity will be adjusted for the secondary endpoints. All data analysis will be conducted in reproducible fashion and the results will be reported regardless of the statistical significance.

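### Section 11.2 plans a dose-toxicity curve, but reduced doses are reached only after toxicity: unadjusted it is likely to mislead, and about 33 subjects are too few to adjust it

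*Combined protocol and SAP*

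**What the plan says.** Section 11.2 ends with two commitments: "Safety data will be summarized for the overall subject group and by dose levels", and "Dose-toxicity curves will be fitted to the final data to estimate the toxicity rates of each dose levels".

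The trial does not assign dose levels. It is single-arm and non-randomised, Section 5.1 starts everyone at 35 mg/m² twice daily, and Section 12.1 sizes the trial on "33 evaluable subjects who will receive the same level of dose". Lower levels arise only through Section 5.4: "A maximum of three dose reductions in decrements of 5 mg per square meter are allowed for toxicity", to a floor of 20 mg/m², and "Do not escalate dose once it has been reduced". Table 3 in Section 5.4.2 takes a subject off treatment at the fourth qualifying non-hematologic event. Not every event leads to a reduction. For toxicities judged unlikely to become serious, footnote a to Table 3 says "subjects may continue on study medication at the same dose without reduction or interruption at the discretion of the Investigator".

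The toxicity population is defined in Section 12.1: "A subject is considered eligible for toxicity evaluation if they have received at least one dose of TAS-102". Section 12.3 says toxicity rates "will also be estimated along with exact 95% binomial confidence intervals". Neither Section 11.2 nor Section 12 names a model for the curve, the toxicity endpoint, the unit (subject or cycle), how an event is attributed to a dose level, or any allowance for dose depending on earlier toxicity.

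**The concern.** A dose-toxicity curve can be read as a dose effect when the subjects at each dose are comparable. Here they are not. Anyone observed at 30 mg/m² has already had a dose-reducing toxicity at 35, anyone at 25 has had two, and so on. Dose is mixed with susceptibility, and also with cycle number, because reduced doses occur only in later cycles.

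Safety and tolerability is a secondary objective (Section 2.2). A flat or rising curve towards the lower doses could be reported as evidence that reducing the dose does not reduce toxicity, when it shows only who was left at those doses.

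**Working it through.** **1. The plan's own figure.** The documents give no figure for the curve. The sample size (Section 12.1) is for PFS: one-sample log-rank test, one-sided alpha 0.10, power 80%, median 6 against 9 weeks, exponential. Without censoring, the expected observed count per subject is 1, the expected null cumulative hazard is 9/6 = 1.5, and the standard deviation under the alternative is 1.5:

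n = (1.2816 × √1.5 + 0.8416 × 1.5)² / (1.5 − 1)² = (1.570 + 1.262)² / 0.25 ≈ 32.1, rounded up to 33.

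Then 33/0.9 = 36.7, so 37 accrued. Both figures reproduce. Nothing in this calculation concerns toxicity by dose.

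**2. Illustration model.** logit p = a + j·ln(0.6) + u, where j is the number of reductions so far, u ~ N(0, SD²) is subject susceptibility, and a is set so that the population rate at the starting dose is 30%. Each event lowers the dose one level, and an event at the lowest level ends treatment. Up to 6 cycles (the maximum anticipated in Section 12.1), with 65% continuing after each cycle; 600,000 subjects per scenario. The 30%, the odds ratio 0.6, the 65% and the SDs are assumptions, as is the simplification that every event triggers a reduction.

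Check at SD 0: the starting odds are 0.30/0.70 = 0.4286. Multiplying by 0.6 each time gives 0.2571, 0.1543 and 0.0926, i.e. 20.5%, 13.4% and 8.5%, as in the table.

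**3. Per-cycle rates (%) at 35/30/25/20 mg/m².**

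| SD | True | Unadjusted |
|---|---|---|
| 0 | 30.0 / 20.5 / 13.4 / 8.5 | 29.9 / 20.4 / 13.3 / 8.6 |
| 0.5 | 30.0 / 20.8 / 13.8 / 8.9 | 28.9 / 22.2 / 16.7 / 12.8 |
| 1 | 30.0 / 21.7 / 15.1 / 10.1 | 26.6 / 25.9 / 24.7 / 24.3 |
| 1.5 | 30.0 / 22.7 / 16.7 / 11.8 | 24.5 / 30.4 / 33.4 / 35.6 |

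There is no bias at SD 0. The curve is nearly flat at SD 1 and reversed at SD 1.5.

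**4. Per-subject rates (at least one episode at that level).** Unselected subjects against those actually observed at the level: SD 1, 50/38/25/14% against 50/46/40/35%; SD 1.5, 47/37/26/16% against 47/52/52/49%. The starting dose is unbiased in this form; the reduced doses are still overstated.

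**5. Events that do not trigger a reduction (SD 1).** With susceptibility correlated 0.5 with that for triggering events, unadjusted rates are 28/24/20/17% against true rates of 30/22/15/10%. With correlation 0 there is no bias.

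**6. Lower toxicity rates.** Here subjects stay on treatment according to a 9-week median PFS and 8-weekly scans. The odds ratio is 1.5 per 5 mg/m² upward (1/1.5 = 0.67 per reduction) and SD is 1:

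| Rate at 35 mg/m² | True (%) | Unadjusted (%) | Expected of 33 ever at 30/25/20 |
|---|---|---|---|
| 10% | 10.0 / 7.1 / 5.0 / 3.4 | 8.9 / 11.3 / 13.2 / 15.3 | 7.1 / 1.1 / 0.1 |
| 20% | 20.0 / 14.9 / 10.9 / 7.8 | 17.2 / 19.5 / 20.9 / 22.4 | 12.2 / 3.0 / 0.7 |
| 30% | 30.0 / 23.3 / 17.6 / 13.0 | 25.7 / 27.0 / 27.6 / 28.3 | 16.4 / 5.3 / 1.6 |

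With a steeper slope (odds ratio 2.0 per 5 mg/m², 20%, SD 1) the unadjusted curve does fall, but too little: 17/16/14/13% against a true 20/12/7/4%. In every scenario run with SD of 1 or more, toxicity was understated at 35 mg/m² and overstated at each lower level.

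**7. Can adjustment rescue it?** A random-intercept logistic model was fitted to 600 simulated trials of 33 subjects under the step 2 assumptions (true odds ratio 0.6 per reduction):

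| SD | 5th / 50th / 95th percentile of OR | OR above 1 | No cycle at lowest level |
|---|---|---|---|
| 1 | 0.09 / 0.55 / 1.38 | 15% of trials | 52% of trials |
| 1.5 | 0.08 / 0.57 / 1.78 | 20% | 38% |

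Under the step 6 treatment-duration model, in four combinations (20% or 30% per cycle, odds ratio 1.5 or 2.0, SD 1 or 1.5), the slope had the wrong sign in 8–24% of trials at N = 33 and 6–20% at N = 37. At N = 33 the central 95% of estimated rates at 20 mg/m² ran from 0–2% up to 39–51%, against true values of 4–15%. At N = 300 estimates centred near the truth, so the obstacle is sample size.

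**8. What is estimable.** In cycle 1 everyone is at the starting dose, so the rate is unbiased (30%) at every SD. For 10 events in 33 subjects the exact 95% interval is 15.6% to 48.7%.

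**The case against.** The strongest reply is that little hangs on this sentence. No stopping rule, dose decision or test uses the curve, and Section 11.2 already supplies overall incidence, severity and attribution tables and listings by subject. That is true. It limits the point to a change that should be made, with no threat to the trial's main conclusions.

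Second, dose level could mean the assigned level. All subjects then sit at one level, no curve can be fitted, and nothing is biased. The wording allows this, but Table 2 labels the reductions as Levels 1 to 3, which favours current dose. On either reading the sentence cannot be carried out usefully.

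Third, 30% per cycle may be high. Section 9.1.3 reports febrile neutropenia in 3.8% of patients in the colorectal study, and Section 5.4.3 reduces dose for hematologic toxicity only under restricted conditions. The objection to the rate is fair, which is why step 6 goes down to 10%. There the direction is unchanged and the two lowest levels are nearly empty, so sparse data become the main problem. That also argues for dropping the curve.

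Fourth, a flat or reversed curve needs substantial heterogeneity. At SD 0.5 the unadjusted curve still falls, and the documents give no SD. This stands: the mechanism is firm, the size is not.

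**Conclusion.** The concern holds. If dose level means current dose, following Section 11.2 without adjustment gives a confounded estimate whenever subjects differ in susceptibility to dose-reducing toxicity. Per-cycle rates are too low at the starting dose and too high at reduced doses; per-subject rates are too high at reduced doses only. The size depends on assumed inputs: negligible at SD 0, modest at SD 0.5, a nearly flat curve at SD 1 and a reversed one at SD 1.5 under the main illustration. Bias is weaker for events that do not trigger a reduction, and absent if susceptibility to them is unrelated. A random-effects adjustment is valid in principle but too imprecise at this size. The accrual goal reads 33 in the Synopsis and Section 3.1 but 37 in Section 12.1; the conclusion is the same for both. The primary PFS analysis and the overall incidence tables are not touched.

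**What to change.** Delete the dose-toxicity-curve sentence from Section 11.2. Keep the overall incidence tables, with the exact intervals of Section 12.3, for all subjects who took at least one dose, as the safety estimate for the regimen that starts at 35 mg/m² with reductions as permitted. Add cycle 1 toxicity rates with the same exact intervals, stating that they omit later toxicity, and the proportions of subjects with 0, 1, 2 and 3 reductions. Label any table by current dose as descriptive and conditional on earlier toxicity.

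If the sponsor wishes to keep a curve, Section 11.2 should name the model (subject random effect and cycle number), the toxicity endpoint and the unit of analysis, and call the result exploratory.

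The cost is one sentence removed, two short table rows added and one table relabelled. What is lost is an exploratory curve that about 33 subjects could not estimate usefully. No dose or clinical rule changes.

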11.3 Methods and Timing for Assessment and Recording Safety Variables

The investigator is responsible for ensuring that all AEs and SAEs that are observed or reported during the study are recorded on the CRF and reported to Taiho in accordance with protocol instructions and clinical trial agreement.

11.4 Type and Duration of Follow-up of Adverse Events

All AEs and SAEs that are encountered during the protocol-specified AE reporting period should be followed to their resolutions, or until the investigator assesses them as stable at the time of the 30-day safety follow-up, or the subject is lost to follow-up. Resolution of AEs and SAEs (with dates) should be documented on the appropriate AE or SAE CRF page and in the subject's medical record to facilitate source data verification.

For some SAEs, the Sponsor or its designee may follow-up by telephone, fax, electronic mail, and/or a monitoring visit to obtain additional case details deemed necessary to appropriately evaluate the SAE report (e.g., hospital discharge summary, consultant report, or autopsy report).

12. STATISTICAL METHODS

The following sub-sections provide an overview of the statistical considerations and analyses.

12.1 Sample Size Determination

This is a pilot phase II single-arm study, with a primary endpoint of progression-free survival (PFS), to evaluate efficacy of TAS-102. Additional objective of the study is to evaluate the feasibility and safety of a regimen of daily TAS-102 administered to subjects with metastatic or unresectable pancreatic adenocarcinoma after progression through or intolerance to first- or second-line chemotherapy. The primary efficacy analysis will be an intent-to-treat comparison of the PFS curve with a reference historical control. From past studies³, the median PFS and/or time to progression (TTP) for subjects with metastatic or unresectable pancreatic adenocarcinoma in the second line of treatment is variable ranging from 6 weeks to 22 weeks. Assuming exponential distributions on PFS on both current study population and the referent population, a sample size of 33 evaluable subjects who will receive the same level of dose will ensure to have at least 80% power to detect an improvement of 3 weeks of median PFS (i.e. from 6 weeks to 9 weeks). The sample size and power derivations were based on one-sample log rank test by Wu $(2015)^{14}$ at one-sided significance level of 0.10. It is assumed that the survival time distributions of both groups (historical and this proposed experiment groups) are approximately the Weibull distribution with a shape parameter of ~ 1.0 . Accounting for about $\sim 10\%$ ineligible/inevaluable subjects, the total number of subjects to be accrued to this cohort will be 37, which is expected to be completed within 24 months. Assuming at least the last evaluable subject derives benefit from the anticipated maximal number of 6 cycles, the length of the entire treatment study will be approximately 30 months.

A subject is considered eligible for toxicity evaluation if they have received at least one dose of TAS-102.

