2. OBJECTIVES AND ENDPOINTS

2.1 Primary

• To determine progression free survival (PFS). The primary endpoint, PFS, is defined as the duration of time from study entry to time of progression or death or the date of last contact, whichever occurs first.

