5. STUDY TREATMENT

All subjects entering the screening phase will receive a unique subject number. This number will be used to identify the subject throughout the study. Subjects withdrawn from the study will retain their subject number.

5.1 Treatment Schedule/Administration:

Treatment must begin within 28 days of the date the subject is entered into the CTMS (OnCore). Upon confirmation of eligibility and provision of subject study number, subjects will receive TAS-102 at the following dose and schedule. The number of tablets of each strength that are needed for the 35 mg/m² dose per BSA level is shown in Table 1.

| TAS-102 | BSA ^a | Dosage in | Total daily | Tablets per dose | |
|----------------------|-------------------|------------|-------------|------------------|-------|
| Dose | (m ²) | mg | dose (mg) | _ | |
| (2x daily) | | (2x daily) | | 15 mg | 20 mg |
| 35 mg/m ² | < 1.07 | 35 | 70 | 1 | 1 |
| | 1.07 - 1.22 | 40 | 80 | 0 | 2 |
| | 1.23 - 1.37 | 45 | 90 | 3 | 0 |
| | 1.38 - 1.52 | 50 | 100 | 2 | 1 |
| | 1.53 - 1.68 | 55 | 110 | 1 | 2 |
| | 1.69 - 1.83 | 60 | 120 | 0 | 3 |
| | 1.84 - 1.98 | 65 | 130 | 3 | 1 |
| | 1.99 - 2.14 | 70 | 140 | 2 | 2 |
| | 2.15 - 2.29 | 75 | 150 | 1 | 3 |
| | ≥2.30 | 80 | 160 | 0 | 4 |
| | | | | | |

 Table 1. Dose Calculations Based off BSA

a Calculate body surface area (BSA) to 2 decimal places.

Each treatment cycle will be 28 days in duration. One treatment cycle consists of the following:

Days 1 through 5: TAS-102 ($35 \text{ mg/m}^2/\text{dose}$) orally 2 times daily with the first dose administered in the morning of Day 1 of each cycle and the last dose administered in the evening of Day 5.

Days 6 through 7: Rest

Days 8 through 12: TAS-102 (35 mg/m²/dose) orally 2 times daily with the first dose administered in the morning of Day 8 of each cycle and the last dose administered in the evening of Day 12.

Days 13 through 28: Rest

The patient must be instructed in the handling of study medication as follows:

- To store the study medication at room temperature
- To only remove from the study medication kit the amount of tablets needed at the time of dosing
- Not to remove doses in advance of the next scheduled dosing
- To make every effort to take doses on schedule
- To take study medication within 1 hour after completing a meal (morning and evening meals) with a glass of water per the dose schedule
- If the patient vomits after taking study medication, the patient should not take another dose.

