g. h. CT of the chest, abdomen and pelvis or CT of the chest and MRI of the abdomen and pelvis are allowed. Consistent imaging modality should be used throughout the study. Imaging should be performed every 8 weeks (+/- 7 days) beginning with Cycle 3 until disease progression.

H&P is required at 30 days (+7 days) following the last dose of study drug. Additional H&Ps are required as needed to follow ongoing AEs.

Adverse events should be followed for 30 days after the last dose of protocol therapy or until the initiation of subsequent treatment. AEs continuing > 30 days should be monitored until resolution.

Subjects or providers should be contacted every 3 months to assess survival status and subsequent therapies.

TAS-102 (Lonsurf[®]) is administered orally twice daily within one hour of completion of morning and evening meals on Days 1 through 5 and Days 8 through 12 of each 28-day cycle.

For CBC w/diff to be obtained at Day 15 of each cycle, notify the investigator if any of the following parameters are observed m. in the lab results: 1) ANC \leq 500 µL, 2) platelets < 50 thou/mm³, or 3) Hgb < 7 g/dL.

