7.5 Follow up/Survival

Please refer to Table 4 located in Section 7.1.

For the purpose of this study, subjects will be seen in follow-up at least every three months until one year after the completion of study treatment. Follow-up evaluations may consist of the interim medical history, physical examination, imaging, CBC, or comprehensive metabolic panel. Any X-rays, CT or MRI scans, or other studies (such as PET scans, bone scans, biopsies, etc.) will be done as clinically indicated and up to the discretion of the treating physician.

After this one-year follow-up period is over, subjects will be continued to be followed for survival until death, withdrawal, or lost to follow up. If subjects are lost to follow-up, every effort will be made at least quarterly to attempt to locate that subject and to determine their health status.

For subjects that come off protocol for reasons other than progressive disease, then CT or MRI scans will be performed every 8 weeks to document disease progression. until disease progression is shown or another anti-cancer therapy is initiated.

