8.4 Confirmation

In non-randomized trials where response is the primary endpoint, confirmation of PR or CR must be confirmed by repeat measurements that should be performed no less than 4 weeks after the criteria for response are first met. In this trial, as overall response rate is a secondary endpoint, confirmation of response in the form of a PR or CR will occur 8 weeks after the criteria for response are first met, since restaging imaging per the protocol will be performed every other chemotherapy cycle (ie every 8 weeks).

In randomized trials or studies where the primary endpoints are stable disease or progression, confirmation of response is not required. Elimination of the requirement for response confirmation may increase the importance of central review to protect against bias, particularly in studies which are not blinded.

In the case of SD, follow-up measurements must have met the SD criteria at least once after study entry at a minimum interval of 6-8 weeks.

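### The one-sided 0.10 of the primary PFS comparison is not assured: the 6-week benchmark has no stated assessment schedule, while this trial looks for progression on 8-week scans

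*Combined protocol and SAP*

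**What the plan says.** Section 12.1 defines the main analysis: "The primary efficacy analysis will be an intent-to-treat comparison of the PFS curve with a reference historical control". The sizing uses a one-sample log-rank test with exponential PFS (Weibull shape about 1) at one-sided 0.10, and claims "at least 80% power to detect an improvement of 3 weeks of median PFS (i.e. from 6 weeks to 9 weeks". This gives 33 evaluable subjects and 37 accrued. The benchmark comes from past studies whose median PFS and/or TTP "in the second line of treatment is variable ranging from 6 weeks to 22 weeks". No assessment schedule is given for them.

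Footnote h to Table 4 (Section 7.1) sets this trial's schedule: "Imaging should be performed every 8 weeks (+/- 7 days) beginning with Cycle 3 until disease progression". Section 8.4 describes the same interval: "restaging imaging per the protocol will be performed every other chemotherapy cycle (ie every 8 weeks". After treatment stops without progression, Section 7.5 continues scans "until disease progression is shown or another anti-cancer therapy is initiated".

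Section 2.1 defines PFS as the "duration of time from study entry to time of progression or death or the date of last contact, whichever occurs first". Study entry is not defined. Section 5.1 adds: "Treatment must begin within 28 days of the date the subject is entered into the CTMS (OnCore".

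Section 12.3 plans Kaplan-Meier mean estimates and curves for PFS. Neither 12.1 nor 12.3 has a rule for events known only to lie between two scans, a match to the benchmark's schedule, or a sensitivity analysis for scan timing.

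**The concern.** A progression found at a scheduled scan is dated at that scan, later than it happened. In a randomised trial with equal schedules, both arms carry the same delay. Here the comparator is a fixed smooth curve, so the delay cancels only if the 6-week figure already contains a similar one.

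Counted from treatment start, the first scheduled scan falls at 8 ± 1 weeks, after the null median and close to the target. An observed median of 6 weeks can arise only if half the subjects die or are found to progress off schedule before any scheduled scan. If PFS starts at registration, a lag of up to 28 days puts the first scan anywhere from week 7 to week 13 (8 + 1 + 4).

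What is at stake is the meaning of a significant result. If the benchmark was read more finely than this trial, an inactive drug can look better than 6 weeks. If it was read as coarsely or more so, the test becomes conservative.

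**Working it through.** **The plan's own figure.** Inputs from 12.1: medians 6 and 9 weeks (hazard ratio 6/9 = 0.667), one-sided 0.10, 80% power, accrual 24 months (104 weeks), then 30 − 24 = 6 months (26 weeks) of follow-up.

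n = (√p0 · z0.90 + σ1 · z0.80)² / (p0 − p1)²

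Under the target, the event probability is p1 = 0.983. The expected null cumulative hazard is p0 = 1.5 × 0.983 = 1.475, and σ1² = 2.140. Then n = (1.214 × 1.2816 + 1.463 × 0.8416)² / 0.4916² = 32.2, rounded up to 33. Power at 33 is 80.7%, and 33/0.9 = 36.7 gives 37. The arithmetic is right.

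**Effect of scan dating.** Assumptions not in the documents: complete follow-up, n = 33, an inactive drug, the test form (O − E)/√E with rejection below −1.2816, and a share q of events dated at the next 8-week scan with the rest dated exactly.

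Suppose first that 6 weeks is a true median.

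- The null hazard is λ0 = ln 2/6 = 0.1155 per week, so the mean is 6/ln 2 = 8.66 weeks.
- The mean scan-dated time is 8/(1 − e^(−8λ0)) = 8/(1 − 0.397) = 13.26 weeks.
- Expected events per subject are then (1 − q) + q × 0.1155 × 13.26 = 1 + 0.532q.
- At q = 0.5, E = 33 × 1.266 = 41.8 and the statistic centres at (33 − 41.8)/√41.8 = −1.36, so about half of null trials reject.
- At q = 0.25, E = 37.4 and the centre is −0.72. At q = 0.10, E = 34.8 and the centre is −0.30.

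Suppose instead that the benchmark was itself read on scans every g weeks. One way to match it is to choose the true rate λ so that the observed mean equals that of an exponential with a 6-week median:

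(1 − q)/λ + q · g/(1 − e^(−λg)) = 8.66

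For g = 6 and q = 0.5, λ = 0.144: 0.5/0.144 + 0.5 × 6/(1 − 0.421) = 3.47 + 5.18 = 8.65. On 8-week scans the same subjects have an observed mean of 3.47 + 0.5 × 8/(1 − 0.316) = 9.32. So E = 33 × 0.1155 × 9.32 = 35.5 and the centre is −0.42. For g = 8 the centre is 0 by construction.

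Simulated size at nominal 0.10 (exact dates: 0.08, with power 0.83):

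| Benchmark read as | q = 10% | 25% | 50% | 75% |
|---|---|---|---|---|
| true median | 0.13–0.14 | 0.24–0.25 | 0.51–0.52 | – |
| 4-week scans | 0.10 | 0.14 | 0.24 | – |
| 6-week scans | 0.09 | 0.10 | 0.12 | 0.14 |
| 8-week scans | 0.08 | 0.06 | 0.04 | 0.01 |

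**Sensitivity to the assumptions.**

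- Matching the benchmark's median instead of its mean, for 8-week scans, requires (1 − q)F(6) = 0.5. True medians are then 5.13, 3.79 and 2.32 weeks at q = 10, 25 and 40%, and size is 0.02 or less.
- With a true 6-week median, an entry-to-treatment lag of 0 to 4 weeks and the ± 7-day window, size is 0.14 / 0.30 / 0.65 at q = 10 / 25 / 50%.
- A second model dates every progression at the next scan and every death exactly. With 10 to 75% deaths and mean matching, size runs from 0.49 to 0.12 for a 4-week benchmark schedule, 0.15 to 0.09 for 6 weeks, and 0.005 to 0.065 for 8 weeks. The pattern is the same.

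**The case against.** The strongest reply is that the 6 weeks comes from published studies and is therefore an observed median, which already contains some scan delay. This stands. It makes the true-median row the least apt of the four. On a 6-week benchmark schedule the size is close to nominal, and the documents do not exclude that case.

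A reader might infer that the false-positive rate is grossly inflated. With a true 6-week median and every event dated at a scan, size is 0.97. The documents do not support that as a description of this trial: deaths count as events and carry their own dates, off-schedule findings are possible, and nothing shows that the benchmark is a continuously observed median.

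A reader might also infer that no primary test exists, because 12.3 lists only Kaplan-Meier summaries. That goes too far. Section 12.1 names the comparison, the test used for sizing and the significance level. The Synopsis plans Kaplan-Meier estimates for PFS, from which a median can be read.

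Nor does it follow that the log-rank test must be replaced. An interval-censored test that censors subjects without an event at the last progression-free scan has its own weakness. Section 8.3 expects symptomatic deterioration without objective progression, and Section 7.5 ends scans at new therapy. If 5 / 10 / 20% of progressions are lost this way (an assumption), that test's size rises to about 0.12–0.13 / 0.16 / 0.27–0.28.

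Finally, this is a self-described pilot, and choosing 6 from a 6 to 22 week range may matter more than scan timing. That is fair, but the plan still claims 80% power at a stated alpha for its primary comparison.

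**Conclusion.** The concern holds in a limited form. The sample-size arithmetic is correct, but the stated one-sided 0.10 is not assured for the data this schedule will produce. The null is a smooth 6-week curve of unstated assessment schedule, and the first scheduled scan lies between the null and target medians. Depending on the benchmark's schedule and the scan-dated share, the planned test's size runs from about 0.01 to 0.14 when the benchmark was read on 6- or 8-week scans. It reaches about 0.24 on 4-week scans, and about 0.5 if 6 weeks is a true median and half the events are scan-dated. Neither quantity is in the documents, so they establish neither inflation nor conservatism, and some cases are near nominal.

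Separately, and from the text alone, a Kaplan-Meier mean is the wrong summary for a hypothesis about medians: under the exponential null the mean is 8.66 weeks when the median is 6. The PFS origin and the role of last contact are also left open. The point deserves correction before analysis. It does not invalidate the design.

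**What to change.** 1. In 12.3, replace the Kaplan-Meier mean with median PFS and a confidence interval.
2. In 12.1, state the source and assessment schedule of the 6-week benchmark. Report the type I error and power of the one-sample log-rank test under this trial's scan schedule, over a stated range of benchmark schedules and scan-dated shares.
3. In 12.3, add a prespecified schedule-based analysis of the primary comparison: an interval-censored exponential likelihood-ratio test, or a one-sample log-rank test against a null curve placed on each subject's scan dates. For deaths and off-schedule progressions, end the interval at the next due scan. Add a sensitivity analysis that counts symptomatic deterioration or new anti-cancer therapy before a scan as an event instead of censoring it. Making this the primary test is optional, and only after step 2 has fixed the null. If the null stays at 6 weeks when the benchmark's true median is 5 or 4, power for a 1.5-fold gain falls to 0.48 or 0.09.
4. In 2.1, count PFS from one defined origin and treat last contact as a censoring date, never as an event.

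The cost is more analysis work and possibly a less favourable stated alpha or power. No scans or subjects are added. If 6 weeks is a true median, the interval-censored test has size about 0.09 and power about 0.82 at n = 33, falling to about 0.78 with 11 to 14% drop-out.
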